4.3 Study Hypothesis

The Oxford Acute Myocardial Infarction - Pressure-controlled Intermittent Coronary Sinus Occlusion in STEMI (OxAMI-PICSO) study aims to analyze the potential benefit of PICSO in a selected population of STEMI patients. In patients with pre-stenting high IMR, and thus with larger infarct size and more compromised microvasculature status, PICSO treatment added to the conventional revascularization gold standard is expected to be associated to a better myocardial reperfusion. This will be assessed by measurement of indexes of coronary physiology and by CMR evaluation of indexes associated to infarct size, myocardial salvage and microvascular obstruction, and other biomarkers. The comparator group will be matched participants previously enrolled in the OxAMI study, with STEMI and with a pre-stenting IMR above 40.

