4.0	06.05.2016	
 - Change in information about regulatory status of PICSO technology from CE-marked to non non-CE mark - Extension of recruitment beyond the period specified in the IRAS application form 	V3.0 20.06.2016
5.0	26.02.2018	
 - Extension of recruitment beyond the period specified in the IRAS application form - Extension of inclusion criteria to allow enrolment of all patients with ST elevation myocardial infarction, irrespectively of the coronary location of the culprit lesion 	V4.0 06.05.2016

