5. OBJECTIVES AND OUTCOME MEASURES/ENDPOINTS

Objectives	Outcome Measures/Endpoints
------------	----------------------------

Primary Objective
 
To assess the impact of PICSO on coronary physiology parameters, on infarct size, on myocardial salvage and on microvascular obstruction at CMR in a selected population of STEMI patients at higher risk of no reflow and with the theoretical prerequisites that make more likely to respond to PICSO treatment. The control group will be represented by a highly matched group of patients from the ongoing Ox-AMI (Oxford Acute Myocardial Infarction) project (Ethics Ref 11/SC/0397), who have undergone all other aspects of the study protocol, including assessment of coronary physiology at 24 hours post primary PCI, 24-48 hours and 6 months CMR, but who have not received PICSO treatment.
	
Area at risk, Infarct size, Myocardial salvage and microvascular obstruction measured by cardiac magnetic resonance at 24-48 hours

Secondary Objectives
 
The OxAMI-PICSO study aims to evaluate the utility of individual biomarkers (blood components derived substances from cells, DNA, plasma etc) in the assessment of coronary artery disease and myocardial infarction. The OxAMI-PICSO may show also how these individual biomarkers may be modified by PICSO treatment.
	
Coronary flow reserve (CFR), Fractional Flow reserve (FFR), index of microcirculatory resistance (IMR) measured at 24 hours after PCI.
 
Infarct size and microvascular obstruction extent measured by cardiac magnetic resonance at 6 months
 
Individual Biomarkers related to coronary artery disease/myocardial infarction at three time points (PCI, 24/48 hours after PCI and 6 months). These include: blood biomarkers of myocardial injury, metabolism and inflammation.

Tertiary Objectives
 
To evaluate the rate of PICSO failure deployment, coronary sinus complications, and additional time and radiation exposure associated to for PICSO deployment
	
Rate of PICSO failure deployment
 
Rate of coronary sinus complications: perforation, dissection, thrombosis
 
Time for PICSO deployment / additional screening time and radiation dose

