6. TRIAL DESIGN

The OxAMI-PICSO study is a prospective single centre observational cohort study of the use of PICSO in patients presenting for primary PCI for acute myocardial infarction. The OxAMI- PICSO study is based upon the established framework of the OxAMI study (Ethics Ref 11/SC/0397).

Patients, age 30-90, presenting with ST elevation myocardial infarction will be considered for inclusion in the study. Measurement of IMR before stenting is an essential prerequisite for the study: only patients with pre-stenting IMR > 40 will be considered eligible for the PICSO treatment. Patients with IMR≤ 40 will remain in the study but will not undergo PICSO treatment. The procedure for consent in patients undergoing emergency PCI will be as already established in the ongoing OxAMI study, and is discussed below in Section 8.1.2.

The PCI procedure will be undertaken in a standard fashion, and include the use of pressure wire measurements before and after stent deployment. Aspiration or distal protection devices may be used if clinically indicated and where vessel anatomy is suitable. The devices used and the procedural techniques will be driven by clinical decision making at the patient and institutional level, and carried out in accordance with the Oxford University Hospitals NHS Trust (OUHT) departmental guidelines for PCI.

PICSO treatment will be added on top of the conventional treatment.

The protocol will constitute of 5 main stages described in details in the next sections (Section 8.3).

Only patients with pre-stenting IMR > 40 and who assent to receive PICSO treatment will undergo 24 hours coronary angiogram with coronary physiology measurement, 24-48 hours CMR scan and 6 months CMR scan. Patients who assent to participate in the study but in whom the pre-stenting IMR ≤ 40, or those in whom the pre-stenting IMR > 40 but the participant declines PICSO treatment will remain in the study for blood sampling and clinical data collection at the same follow up time points (24 hours, 48 hours and 6 months). A summary of the study design, indicating the time points and procedures, is shown in Section 8.3.

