8.3 Study timeline (see “Integrated flowchart for OxAMI-PICSO study” as below)

The OxAMI-PICSO study will take place beside an ongoing large prospective observational study in STEMI patients (OxAMI study). Patients fulfilling the OxAMI-PICSO criteria will be invited to participate in the study. OxAMI-PICSO study will constitute of 5 main stages:

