The PICSO Impulse Catheter is then connected to the PICSO Impulse console. The PICSO Impulse Console automatically operates the PICSO Impulse Catheter. The balloon is intermittently inflated and deflated using helium, based on coronary sinus pressure and synchronized with the ECG. The monitor displays the inflation/ deflation state of the balloon, as well as trend graphs and time counters; Live graphs display curves and numeric values of ECG, coronary sinus pressure, aortic pressure and auxiliary input. It is easy to use and provides direct feedback on the patient's individual therapy using the 'PICSO Dose', which is defined as the sum of the coronary sinus pressure modulation for all PICSO cycles applied. All data are automatically stored and can be retrieved for later analysis for each patient. The unit is transportable and runs on battery supply if needed during patient transportation.

Once the PICSO Impulse catheter is connected to the consoled, by activating the "START" button, the distal balloon will be cyclically inflated. Each cycle starts with a balloon inflation triggered by QRS

complex on ECG monitoring. During balloon inflation coronary sinus pressure will progressively increase till reaching a plateau, then coronary sinus occlusion is stopped by balloon deflation. For security, each balloon inflation has a maximum limit of 30 seconds in duration. The deflation interval between two cycles has a minimum duration of 3 seconds.

In the OxAMI-PICSO the PICSO Impulse system will be adopted in a highly selected population of patients with ST elevation myocardial infarction, characterized by a possibly impaired microvasculature impairment at the time of the PCI, as expressed by a prestenosing elevated index of microcirculatory resistance (> 40). The aim is to assess the extent of infarct size after 24-48 hours in such specific group of patients. Propensity-score matched historical patients from the ongoing OxAMI study will be controls in the OxAMI-PICSO study.

All the investigators using the PICSO device will undergo a specialist training programme completion, including the performance of the first cases under the supervision of a proctor expert. Educational training sessions for use of the PICSO will be provided to all clinical staff (nurses, radiographers, physiologists) involved in the care of patients who have received PICSO.

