12.2 Analysis of Endpoints

In keeping with our usual practice we will obtain expert statistical advice from the Centre for Statistics in Medicine (or equivalent) for each specific task. Summary statistics, including means, medians, and

variances, will be calculated at each time point and for each type of data (e.g. parameters derived from coronary physiology and CMR). The distribution of the levels will be described. It may be necessary to log transform the data before further statistical analysis. For each parameter an analysis of variance will be carried out at each time point.

Control group in OxAMI-PICSO study is represented by a highly matched group of patients underwent to primary PCI, with a prestenosing IMR > 40 and with available 24 hours recath and 24-48 hours/6 months CMR data. Matching will be performed by application of a propensity score matching analysis including the following predictors in the model: age, sex, pain to wire time, thrombotic burden (assessed as angiographic thrombus score), thrombus aspiration performance, stent volume, glycoprotein IIbIIIa inhibitors adoption.

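### The plan does not settle whether controls may be contemporaneous, leaves enrolment date out of the matching, and has no check for change in care over time

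*Combined protocol and SAP*

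**What the plan says.** The protocol describes the control source in four places, and they differ on dates.

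- Section 4.3: "The comparator group will be matched participants previously enrolled in the OxAMI study".
- Section 10.1: "Propensity-score matched historical patients from the ongoing OxAMI study will be controls in the OxAMI-PICSO study".
- Section 5: a "highly matched group of patients from the ongoing Ox-AMI (Oxford Acute Myocardial Infarction) project", with no date limit.
- Section 12.2: matched primary PCI patients with pre-stenting IMR above 40 and available 24-hour angiographic and CMR data, again with no date limit.

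Section 8.3 adds that OxAMI is still running beside this study.

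The propensity score in 12.2 uses "age, sex, pain to wire time, thrombotic burden (assessed as angiographic thrombus score), thrombus aspiration performance, stent volume, glycoprotein IIbIIIa inhibitors adoption". Date or period of enrolment is not among these seven. Beyond matching, 12.2 offers descriptive summaries, a possible log transformation and an analysis of variance per time point.

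On the time span, the Synopsis gives a planned trial period of 18 months. Its version table runs from v1.0 (13.02.2015) to v5.0 (26.02.2018), and v4.0 and v5.0 both list "Extension of recruitment beyond the period specified in the IRAS application form".

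On untreated participants within this study, section 6 says "Patients with IMR≤ 40 will remain in the study but will not undergo PICSO treatment". They and those who decline PICSO "will remain in the study for blood sampling and clinical data collection at the same follow up time points". Sections 8.3.4 and 8.3.5 reserve CMR for patients who receive the device.

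**The concern.** The study's own untreated participants have no CMR, so the matched OxAMI group is the only comparator for the primary endpoint. Under 4.3 and 10.1 that group was enrolled before the PICSO patients. Treatment then coincides with calendar period, and any shift in background care or in measurement enters the estimated device effect.

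Such a shift is possible, because section 6 leaves PCI devices and technique to clinical judgement and local departmental guidance. Nothing in 12.2 would reveal it or limit it directly. The unclear wording also leaves room to choose the control pool after infarct sizes are known.

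**Working it through.** **Inputs from the documents.** Section 12.1 gives a 29% relative reduction in infarct size, 95% confidence (read as two-sided 5%), 80% power, and 12 per group raised to 25. No SD or mean infarct size is given, so the 12 cannot be reproduced; it can only be solved backwards.

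**Step 1: implied SD (normal approximation).** From n = 2(1.96 + 0.842)² × (SD/29)² with n = 12:

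SD = 29 / (2.802 × √(2/12)) = 29 / 1.144 = 25.4% of the control mean.

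**Step 2: precision at 25 per arm.** SE = 25.4 × √(2/25) = 7.2 points, treating the arms as independent.

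**Step 3: size of a possible era effect (assumed).** Suppose infarct size falls 1-3% a year for reasons other than PICSO, with a mean gap of 3-5 years.

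- Low end: 1 − 0.99³ = 3.0%, and 3.0/29 = 10% of the planned effect.
- High end: 1 − 0.97⁵ = 14.1%, and 14.1/29 = 49% of the planned effect.

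**Step 4: significant results with no PICSO effect.** With b = era difference / SE, the two-sided rate is Φ(b − 1.96) + Φ(−b − 1.96).

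| Era difference | SD 25.4% | SD 40% (assumed) |
|---|---|---|
| 5% | 11% | 7% |
| 10% | 29% | 14% |
| 15% | 55% | 26% |

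For example, at 10% and SD 25.4%, b = 10/7.2 = 1.39 and the rate is about 29%.

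**Step 5: which remedies work (simulation, all settings assumed).** Take 25 PICSO patients spread over 3 years, 80 controls over the preceding 3.5 years, a linear fall of 3% a year, SD 25.4% and no device effect.

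- Date ignored: the mean gap is 1.5 + 1.75 = 3.25 years, so the expected bias is 3.25 × 3 = 9.75 points. The simulation gave −9.7 points and 27% false positives.
- The 25 most recent controls: −6.0 points and 13%.
- Date as a covariate over the whole pool: bias about 0 and 5%. The SE rises from 0.072 to 0.102 of the control mean, and the trend is assumed linear.
- Date added to the propensity score: with no overlap in dates, only about 1.6 of 25 pairs could be matched. With 30% of controls concurrent, about 19 pairs were matched; bias fell from −7.8 to about +1 point and false positives from 16% to about 4%.
- Power to detect a 3% a year trend inside a pool of 50-100 controls is about 14-22%.

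Date in the score therefore helps only if dates overlap, and a non-significant trend test would not exclude drift.

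**The case against.** Several points on the other side stand.

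- A reader might infer that the plan confines controls to past patients. Sections 4.3 and 10.1 read that way, but the statistical definition in 12.2 and the objective in 5 carry no such limit, and 10.1 itself calls OxAMI ongoing. The supportable point is that eligibility by date is unsettled.
- Pain to wire time, thrombus aspiration and glycoprotein inhibitor use are in the score and may capture part of any change in practice. Section 5 also requires controls to have followed the rest of the protocol. This reduces the problem by an unknown amount and does not remove it.
- A reader might also infer that the IMR ≤ 40 recruits, who never receive PICSO, could measure the drift so that it can be subtracted. They have no CMR, so they say nothing direct about infarct size, and drift in IMR or a biomarker is on another scale. Section 4.1 reports that patients with low pre-stenting IMR show little change in IMR, so a null result there could falsely reassure.
- Contemporaneous controls may be scarce. Section 8.3 invites eligible patients into this study, and those with IMR above 40 who decline PICSO get no CMR under section 6.
- The design is openly an observational cohort, and at the low end the assumed bias is only 3%.

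These points narrow the remedy and lower the severity. They do not supply a date rule or an era check.

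**Conclusion.** The concern holds as a should-fix. The sections disagree on whether controls must predate the PICSO patients, date is not used in matching, and no sensitivity analysis for era is planned. A change in care over time could therefore be read as a PICSO effect on infarct size.

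The documents do not show that care changed, in which direction, or by how much; they also give no enrolment dates for either group. The 3-14% range rests wholly on the assumed 1-3% a year and 3-5 year gap. The false-positive rates also depend on an SD inferred from the 12 per group. It would go too far to say that the comparison is known to be biased, or that the study's own untreated patients can correct it.

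**What to change.** 1. In 4.3, 10.1 and 12.2, use one definition of the control pool: all OxAMI patients with pre-stenting IMR > 40 and the required 24-hour and CMR data, including any enrolled during PICSO recruitment. Fix it before outcomes are examined.
2. Among acceptable propensity matches, take the closest enrolment date, and report enrolment dates by group. Do not rely on date in the propensity score unless the dates overlap.
3. Add sensitivity analyses of infarct size: enrolment date as a covariate across the dated OxAMI pool and, if numbers allow, a comparison restricted to concurrent or most recent controls.
4. Optionally, compare IMR ≤ 40 recruits with OxAMI patients in the same IMR stratum on end-of-PCI IMR, and on biomarkers if measured alike. Treat this as descriptive for those outcomes only. Do not subtract the result from the infarct-size effect, or read a null result as absence of drift.

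The cost is wording in three sections and a few extra analyses, with no new patient procedures. Concurrent untreated patients with CMR may be few or selected, and date adjustment widens the interval and assumes a linear trend. These analyses therefore support the main comparison and do not replace it.

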5. OBJECTIVES AND OUTCOME MEASURES/ENDPOINTS

Objectives	Outcome Measures/Endpoints
------------	----------------------------

Primary Objective
 
To assess the impact of PICSO on coronary physiology parameters, on infarct size, on myocardial salvage and on microvascular obstruction at CMR in a selected population of STEMI patients at higher risk of no reflow and with the theoretical prerequisites that make more likely to respond to PICSO treatment. The control group will be represented by a highly matched group of patients from the ongoing Ox-AMI (Oxford Acute Myocardial Infarction) project (Ethics Ref 11/SC/0397), who have undergone all other aspects of the study protocol, including assessment of coronary physiology at 24 hours post primary PCI, 24-48 hours and 6 months CMR, but who have not received PICSO treatment.
	
Area at risk, Infarct size, Myocardial salvage and microvascular obstruction measured by cardiac magnetic resonance at 24-48 hours

Secondary Objectives
 
The OxAMI-PICSO study aims to evaluate the utility of individual biomarkers (blood components derived substances from cells, DNA, plasma etc) in the assessment of coronary artery disease and myocardial infarction. The OxAMI-PICSO may show also how these individual biomarkers may be modified by PICSO treatment.
	
Coronary flow reserve (CFR), Fractional Flow reserve (FFR), index of microcirculatory resistance (IMR) measured at 24 hours after PCI.
 
Infarct size and microvascular obstruction extent measured by cardiac magnetic resonance at 6 months
 
Individual Biomarkers related to coronary artery disease/myocardial infarction at three time points (PCI, 24/48 hours after PCI and 6 months). These include: blood biomarkers of myocardial injury, metabolism and inflammation.

Tertiary Objectives
 
To evaluate the rate of PICSO failure deployment, coronary sinus complications, and additional time and radiation exposure associated to for PICSO deployment
	
Rate of PICSO failure deployment
 
Rate of coronary sinus complications: perforation, dissection, thrombosis
 
Time for PICSO deployment / additional screening time and radiation dose

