2. SYNOPSIS

Trial Title	Oxford Acute Myocardial Infarction - Pressure-controlled Intermittent Coronary Sinus Occlusion in STEMI
Internal ref. no. (or short title)	OxAMI-PICSO
Clinical Phase	II
Trial Design	Prospective single centre observational cohort study

Trial Participants	Patients admitted for primary percutaneous coronary intervention for ST elevation myocardial infarction	
Planned Sample Size	75 patients	
Treatment duration	Maximum of 90 minutes	
Follow up duration	6 months	
Planned Trial Period	18 months	
	Objectives	Outcome Measures/Endpoints
Primary	To evaluate the effect of pressure intermittent controlled coronary sinus occlusion on the indexes of coronary physiology and on infarct size in STEMI patients at short and mid term follow up.	To evaluate the effect of pressure intermittent controlled coronary sinus occlusion on infarct size measured at cardiac magnetic resonance after 24-48 hours from revascularization.
Secondary	To evaluate the utility of individual biomarkers (blood components derived substances from cells, DNA, plasma etc) in the assessment of coronary artery disease and myocardial infarction investigating also how these individual biomarkers may be modified by PICS0 treatment.	To evaluate the effect of pressure intermittent controlled coronary sinus occlusion on humoral biomarkers and on the evolution of parameters of coronary physiology at 24 hours and infarct size, microvascular obstruction at cardiac magnetic resonance after 6 months from revascularization.
Safety Endpoint	To evaluate the rate of PICS0 failure deployment, coronary sinus complications, and additional time and radiation exposure associated to for PICS0 deployment	
Device name	Pressure intermittent controlled coronary sinus occlusion (PICS0)	
Device Manufacturer	Miracor Medical System	
Device Classification	Interventional Cardiology	

Protocol version no.	Effective Date	Significant Changes	Previous protocol version no.
2.0	01.04.2015	- Clarification of follow up duration - Clarification for what group of patient CMR follow up is meant	v1.0 13.02.2015
3.0	20.06.2016	- Extension of sample size to 75 patients to achieve a minimum of 25 patients with complete dataset	v2.0 01.04.2015

Protocol version no.	Effective Date	Significant Changes	Previous protocol version no.

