12 STATISTICS

12.1 Number of Participants

The OxAMI-PICSO study aims to investigate the potential benefit of PICSO in a highly selected population of STEMI patients. In line with the data reported by Sayeed et al in a previous metanalysis on 7 studies about PICSO application in animal models, the recently published Prepare-RAMSES study also observed a 30% reduction in IS in the treatment arm, however such reduction was not statistically significant in comparison to the control arm [19]. The study, however could still show a benefit of PICSO in terms of IS reduction at six months follow up in the subgroup of patients receiving high PICSO quantity. The study, however, was significantly hampered by the inclusion of relative low risk patients and by a small sample size. The author managed indeed to deliver full PICSO treatment only in 63% of the initial planned cohort (12 patients, of the 30 planned, received a prolonged treatment with PICSO) [22].

In order to address the first limitation of the Prepare-RAMSES study, OxAMI-PICSO study will select patients with a preexisting higher IMR. In this way PICSO is meant to be applied only in a population at higher risk and highly likely to get benefit from its application.

In this regard assuming that the stricter inclusion criteria may allow to detect a substantial benefit from PICSO compared to the control group and expecting that this will allow to achieve a significant 29% reduction in IS as shown in Sayeed's metanalysis [19], we initially calculated a final sample size of 12 patients with complete final data per each group with an interval of confidence at 95% and a 80% power. However considering that this was the final same sample size enrolled in the Prepare-RAMSES study, initially meant to recruit 30 patients per arm, we propose to double the actual sample size from 12 to 25 per arm.

Allowing for participants who do not wish to undergo repeat cardiac catheterisation, or cardiac MRI, we anticipate that approximately 75 patients may be recruited to the study in order to achieve full participation and complete follow up in 25 subjects.

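### The primary endpoint is infarct size alone in the synopsis and Section 10.1 but four unranked CMR measures in Section 5, and Section 12.2 designates no primary comparison

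*Combined protocol and SAP*

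**What the plan says.** Two places name one measure at one time. The synopsis gives the primary outcome as the effect of PICSO "on infarct size measured at cardiac magnetic resonance after 24-48 hours from revascularization". Section 10.1 agrees: "The aim is to assess the extent of infarct size after 24-48 hours in such specific group of patients".

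Section 5, the section devoted to endpoints, puts four measures in its primary row: "Area at risk, Infarct size, Myocardial salvage and microvascular obstruction measured by cardiac magnetic resonance at 24-48 hours". None is ranked, and nothing says whether one or all must succeed.

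The objectives are broader than either list of outcomes. The synopsis objective is the effect "on the indexes of coronary physiology and on infarct size in STEMI patients at short and mid term follow up". The Section 5 objective is "To assess the impact of PICSO on coronary physiology parameters, on infarct size, on myocardial salvage and on microvascular obstruction at CMR". Section 4.3 (Study Hypothesis) likewise expects benefit to show in coronary physiology, several CMR indexes and biomarkers. Yet the physiology endpoints, "Coronary flow reserve (CFR), Fractional Flow reserve (FFR), index of microcirculatory resistance (IMR) measured at 24 hours after PCI", stand in the secondary row of Section 5, and the six-month CMR measures are secondary in both places.

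Section 12.1 sizes the study on infarct size, "expecting that this will allow to achieve a significant 29% reduction in IS", without saying when infarct size is measured. Section 16.11 also states the expected benefit for infarct size, again with no time. Section 12.2 plans an analysis of variance on every parameter at every time point, leaves a log transform open, and describes the propensity matching. It does not single out a primary comparison, a testing order or a multiplicity rule.

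**The concern.** A reader of the synopsis and a reader of Section 5 would report different primary results, and the analysis section cannot tell them which is right. Whoever analyses the study could lead with infarct size, salvage or microvascular obstruction, whichever looks best, and cite the protocol for the choice.

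The design makes this matter more. The controls are matched patients from the OxAMI study, selected under Section 12.2 for having their repeat catheterisation and CMR data available. Some comparator outcomes may therefore be known before the primary endpoint is settled. The confidence and power statement in Section 12.1, "12 patients with complete final data per each group with an interval of confidence at 95% and a 80% power", was made for infarct size and cannot be carried over to the other three measures.

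**Working it through.** **1. What each place supports**

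| Place | Infarct size as sole measure? | 24–48 h stated? |
|---|---|---|
| Synopsis, primary outcome | Yes | Yes |
| Section 10.1, aim | Yes | Yes |
| Section 12.1, sample size | Yes | No |
| Section 16.11, benefit | Yes | No |
| Section 5, primary outcome | No, four measures | Yes |
| Synopsis, primary objective | No, adds physiology | No, short and mid term |
| Section 5, primary objective | No, adds physiology, salvage, obstruction | No |
| Section 4.3, hypothesis | No, several kinds of measure | No |

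Four places support infarct size as the sole measure, and two of these also fix the time. Four places are wider. All of this is current text; the amendment log plays no part.

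**2. The plan's own figure.** The 12 per group cannot be reproduced, because neither the SD nor the control mean of infarct size is given. This point does not depend on it.

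**3. Illustration of the open choice**

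From the documents: 25 per arm (Section 12.1) and analysis of variance (Section 12.2), which for two groups is the t-test. The 95% confidence in Section 12.1 is read as two-sided 5%; the sidedness is not stated.

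Assumed, because the documents are silent:
- Success means that any one of infarct size, salvage or microvascular obstruction is significant.
- There is no true effect, and the groups are comparable.
- Salvage = area at risk − infarct size.
- The SD of area at risk is 1.0 or 1.5 times that of infarct size.
- The correlation of area at risk with infarct size is 0 to 0.9.
- The correlation of microvascular obstruction with infarct size is 0 to 0.9. Its correlation with area at risk is either the same value or the product of the other two.

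Area at risk is left out as a route to success. The hypothesis and the Section 5 objective do not name it as something PICSO should change.

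Simple bounds come first. One test gives 5% in either direction, and 5% / 2 = 2.5% in the direction of benefit. Three tests cannot exceed 3 × 5% = 15% and 3 × 2.5% = 7.5%. Simulated null trials (60,000 per setting for the either-direction count) place the result between these bounds. Benefit means a smaller infarct, less obstruction or more salvage.

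| Correlation of obstruction with infarct size | Any of three, either direction | Any of three, benefit only |
|---|---|---|
| 0 to 0.7 | 11.5–14.4% | about 5.7–7.5% |
| 0.9 | 10.1–11.7% | about 5.0–6.0% |
| Infarct size alone | 5% | 2.5% |

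The inflation is about two- to three-fold on either scale: 10.1 / 5 ≈ 2.0 to 14.4 / 5 ≈ 2.9, and 5.0 / 2.5 = 2.0 to 7.5 / 2.5 = 3.0.

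**The case against.** The strongest reply is that the intent is plain. Infarct size is the synopsis outcome, the Section 10.1 aim and the basis of the sample size. The study is labelled Phase II and observational, and Section 12.2 promises expert statistical advice for each task. What stands is that infarct size is the natural choice, so the repair should be uncontroversial. What does not stand is that no repair is needed. Section 5 is the endpoint section and cannot be set aside, the study is powered for a significant result, and later advice does not replace a choice made in advance.

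The four measures might be meant as co-primary. No text says so or states a success rule.

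A fair criticism of the error rate is that counting either direction includes results where PICSO looks worse. The rate that matters for a false claim of benefit is about half as large, so both are shown.

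**Conclusion.** The contradiction is real and must be resolved: one primary outcome has to be named consistently, and Section 12.2 has to name its comparison. The mismatch in the objectives is a lesser part of the same repair. Under the stated assumptions, leaving the choice open would raise the false-positive rate from 5% to about 10–14%, and the rate of false benefit claims from 2.5% to about 5–7.5%. The success rule, correlations, SDs and definition of salvage are assumptions, so these figures illustrate the room left open and do not predict this trial's error rate.

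Four stronger readings are tempting but not supported:
- A reader might see one stray table against an otherwise consistent protocol. Section 4.3 and both primary objectives also cover several measures.
- A reader might take Section 12.1 as confirming the 24–48 h time. It gives none for the 29% reduction, and the human subgroup result it cites is at six months.
- A reader might compute 1 − 0.95⁴ = 18.5% for four independent tests. If salvage is area at risk minus infarct size, the four cannot be independent.
- A reader might infer that the study is underpowered for several endpoints. Without an SD or control mean, the documents cannot show that.

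**What to change.** - **Section 5:** make infarct size by CMR at 24–48 h the sole primary outcome, as in the synopsis and Section 10.1. List myocardial salvage and microvascular obstruction at 24–48 h as secondary. Report area at risk descriptively.
- **Section 12.2:** name the comparison of that outcome with the matched controls as the only primary analysis, at two-sided 5%. A fixed testing sequence for the secondary CMR measures is optional.
- **Synopsis, Section 5 and Section 4.3:** align the primary objectives and the hypothesis with this outcome. Coronary physiology and mid-term follow-up belong with the secondary objectives, where their endpoints already are.
- **Section 12.1:** state that the 29% reduction refers to infarct size at 24–48 h, if that was the intention.

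The cost is wording only, with no new patients or data. The downside is that salvage and microvascular obstruction can no longer be claimed as primary results. The change does not remove bias from the historical controls, so the 5% rate for infarct size still depends on how well the matching works.
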